11.3 Processing Patient Reported Outcomes

Paper based patient reported outcome (PRO) data may be collected from a diary, questionnaires, or other specified document, etc. and entered into the data management system (DMS).

Electronic Patient reported outcome (ePRO) data may be collected using electronic devices and transferred electronically to GSKCH or third-party DM vendor.

All PRO source data should be reviewed by the Study Staff and the Study Monitor in order to ensure accurate transcription of data and that any potential AEs or concomitant medications reported on these documents are discussed with the subject and transcribed accurately to the CRF and/or DMS. PROs that are classed as source data will be retained by the investigator and true/certified copies may be sent to a designated vendor or GSK CH as required.

To protect the privacy of subjects, no Personal Information (PI) (including the subject's name or initials or birth date) is to be recorded on any PRO/ePRO that will be forwarded to GSK CH or third-party Vendor.

In this study subjects will be provided with a diary card to complete during the home use period, following first supervised product use and diary completion. Subject self-assessment responses will be collected directly in the CRF.

12 STATISTICAL CONSIDERATIONS AND DATA ANALYSES

12.1 Sample Size Determination

A sufficient number of subjects will be screened (approximately 180) to randomize 90 subjects to ensure that at least 60 subjects (30 per arm) complete the study. It is deemed that 30 subjects per arm are considered sufficient to assess the primary endpoint of the dermatologist assessment of signs and symptoms of cutaneous irritation total score. The sample size for this study has been selected based on clinical considerations and to ensure compliance with the ANVISA Guideline for the Safety Evaluation of Cosmetic Products which mandates an investigational product be tested on at least 30 subjects.

12.2 Statistical Methods and Analytical Plan

Additional details of the proposed statistical analysis will be documented in the statistical reporting and analysis plan (RAP), which will be written by a GSK approved vendor following finalization of the protocol and prior to study unblinding/analysis (as appropriate).

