3 STUDY OBJECTIVES AND ENDPOINTS

Table 3-1 Study Objectives and Endpoints

| Objective(s) | Endpoint(s) |
|---|---|
| Primary | |
| To determine the local cutaneous tolerance profile of the investigational product in healthy females with sensitive facial skin under normal conditions of use. | Change from baseline (prior to any product application) in dermatologist visual assessment scores of signs and symptoms of cutaneous irritation to 21 (+2) days of product use. |
| Secondary | |
| To determine the local ocular tolerance profile of the investigational product in healthy females with sensitive facial skin under normal conditions of use. | Change from baseline (prior to any product application) in ophthalmologist visual assessment scores of signs and symptoms of ocular irritation to 21 (+2) days of product use. |
| To determine the local cutaneous and ocular tolerance of the investigational | Change from baseline in subject self-assessment scores of signs and symptoms |

| | |
|---|--|
| product from the perspective of the subject in healthy females with sensitive facial skin under normal conditions of use. | of cutaneous and ocular irritation to 1-2 hours after first product application and following 21 (+2) days of use. |
| Safety | |
| To evaluate the general safety of two cosmetic facial serums. | Frequency and severity of Adverse Events. |

The objective of this clinical study is to determine the local tolerance profile of a developmental facial serum product in healthy females with sensitive facial skin under normal conditions of use, following 21 (+2) days twice daily application.

This study will be considered a success if at least 90% of completed subjects do not have a significant increase (i.e. a unit increase score of 1 in the total score) from baseline in dermatologist assessed signs and symptoms of cutaneous irritation following 21 (+2) days of investigational product use.

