3.4 Timepoints and Visit Windows

The timepoints and visits for this study are defined in the section “Schedule of Activities” of the protocol. Any deviation from the study schedule will be reviewed on case-by-case basis to identify any major deviations. A listing of subjects who are non-compliant with the protocol specified time-window for study visits will be produced for the Blinded Data Review Meeting (BDRM).

4 Data Analysis

Data analysis will be performed by Syneos Health. The statistical analysis software used will be SAS (Studio) version 9.4 or higher.

Prior to database closure a BDRM will be conducted, during which various aspects of the trial will be discussed and agreed.

Unless otherwise described, all listings will be produced for all randomized subjects.

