4.1.2 Protocol Deviations

Protocol deviations will be tracked by the study team throughout the conduct of the study. Data will be reviewed prior to unblinding and closure of the database to ensure all important deviations are captured and categorised.

Important deviations of the protocol procedures identified as liable to influence the primary tolerability outcome may include, but will not necessarily be limited to:

- Violation of inclusion or exclusion criteria at screening that may affect primary tolerability.
- Non-compliance with product application.
- Use of prohibited treatment or medication before or during the study which will affect the primary tolerability.
- Violation of the visit window.

Further deviations liable to influence the primary tolerability will be given in the Review Listing Requirement (RLR) document where important deviations will be identified at the BDRM.

The number and percentage of subjects with an important protocol deviation (overall and by type of deviation) will be presented by product group (PPD) and listed in PPD .

All protocol deviations captured on the case report form will be listed in PPD . The listing will present date of deviation, deviation type and deviation description.

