4.4 Analysis of Tolerability

4.4.1 Primary Tolerability Endpoint

4.4.1.1 Primary Tolerability Endpoint Definition

The primary endpoint will be the change from baseline (prior to any product application) in dermatologist signs and symptoms of cutaneous irritation total score following 21 (+2) days of product use.

This study will be considered a success if at least 90% of completed subjects do not have a significant increase (i.e. a unit increase score of 1 in the total score) from baseline in dermatologist assessed signs and symptoms of cutaneous irritation following 21 (+2) days of investigational product use.

Calculation of dermatologist assessment of signs and symptoms of cutaneous irritation total score and change from baseline in total score:

The cutaneous irritation total score will be calculated in the following way:

Cutaneous irritation total score = dermal response score of erythema + dermal response score of dryness + dermal response score of scaling + dermal response score of edema

Where, the dermal response score is described in [Table 4-1](#).

Table 4-1 Dermatological Evaluation

Attribute	Description (Score)				
Erythema	None (0)	Very Slight (0.5)	Slight (1)	Moderate (2)	Severe (3)
Dryness	None (0)	Very Slight (0.5)	Slight (1)	Moderate (2)	Severe (3)
Scaling	None (0)	Very Slight (0.5)	Slight (1)	Moderate (2)	Severe (3)
Edema	None (0)	Very Slight (0.5)	Slight (1)	Moderate (2)	Severe (3)

For example, if the dermal responses score of erythema = 2, dermal responses score of dryness = 0.5, dermal responses score of scaling = 1 and dermal responses score of edema = 0.5.

Then the cutaneous irritation total score will be:

$$\text{Total score} = 2 + 0.5 + 1 + 0.5 = 4.$$

Change from baseline in dermatologist signs and symptoms of cutaneous irritation total score = total score at day 21 – total score at baseline.

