4.4.1.2 Statistical Hypothesis, Model, and Method of Analysis

The dermatologist signs and symptoms of cutaneous irritation total score will be calculated as the sum of the individual dermal response attributes (erythema, dryness, scaling, and edema). The change from baseline in the total score will be summarised by number and percentage of subjects by visit for each product group (PPD [redacted]). Additionally the change from baseline score greater than 1 will be summarised by number and percentage of subjects by visit for each product group. No formal statistical inference will be performed.

The individual attribute responses, total score and change from baseline in total score will be listed for each subject by visit and by product group (PPD [redacted]).

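### The analysis plan need only precede unblinding, which is a weak safeguard for a within-arm success criterion whose cut-off and data-exclusion rules are still open

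*Protocol*

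**What the plan says.** **Timing.** Protocol 12.2 has the RAP written "following finalization of the protocol and prior to study unblinding/analysis (as appropriate". That is the only limit. Sign-off is not tied to enrolment, to the first post-baseline data or to the last visit.

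**Success rule.** Protocol section 3 states: "This study will be considered a success if at least 90% of completed subjects do not have a significant increase". It defines such an increase as "a unit increase score of 1 in the total score", assessed "following 21 (+2) days of investigational product use". SAP 4.4.1.1 repeats the rule. SAP 4.4.1.2 then plans a different count: "Additionally the change from baseline score greater than 1 will be summarised by number and percentage of subjects". SAP Table 5-1, which records departures from the protocol, lists only the definitions of prior and concomitant medication.

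**Exclusions and deviations.** Protocol 12.2.2 leaves the exclusion of any data to a blinded data review meeting (BDRM) before lock and allows none afterwards. SAP 4.1.3 sends exclusions from the Safety population to the same meeting. Neither gives criteria for excluding data. SAP section 4 says: "Prior to database closure a BDRM will be conducted, during which various aspects of the trial will be discussed and agreed". SAP 3.4 has departures from the visit schedule judged individually, and SAP 4.1.2 adds: "Further deviations liable to influence the primary tolerability will be given in the Review Listing Requirement (RLR) document".

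**Masking.** Protocol 6.5 blinds the statistician, data managers and sponsor staff to product allocation. Neither document limits who may see pooled scores.

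**Already fixed in the protocol.** Section 3 sets the 90% level, the completer denominator, the investigational arm and the time point. Section 4.4 defines completion. Section 12.2.6 sets the four-item total, the Safety population and a purely descriptive analysis. Section 12.2.10 rules out imputation.

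**The concern.** Finalising a plan before unblinding is a sound safeguard when the result is a contrast between arms, because nobody can compute the contrast without the code. This study plans no such contrast. Whether a subject's total score rose can be computed for every subject with no code at all. The code hides only which of the pooled increases belong to the serum.

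A plan completed after Visit 2 scores exist may therefore be written by people who can narrow down the verdict. The same holds for exclusions decided at a meeting that sees those scores. If rules that bear on pass or fail are still open then, the claim that the 90% criterion was pre-specified is weaker than it appears.

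**Working it through.** **The plan's own figures.** There is no power calculation to reproduce. The documents give 90 randomised and at least 60 completers, 30 per arm, so 60/90 is two-thirds retained. The allocation ratio is not stated. I assume 1:1, so completers lie between 30 and 45 per arm.

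**Increases allowed.** With 30 completers, 0.9 × 30 = 27 must be free of an increase, so at most 3 may have one. With 45, 0.9 × 45 = 40.5, so 41 are needed and at most 4 may have one.

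**What a pooled count reveals.** Let K be the pooled number of increases. If increases are exchangeable between arms, the number X in the investigational arm is hypergeometric, and P(success | K) = P(X ≤ 3) with X ~ Hypergeom(60, 30, K), or P(X ≤ 4) with X ~ Hypergeom(90, 45, K). For example, at K = 4 with 30 per arm: 1 − C(30,4)/C(60,4) = 1 − 27,405/487,635 = 0.944.

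| Pooled increases K | P(success), 30 per arm | P(success), 45 per arm |
|---|---|---|
| 3 or fewer | 1.00 | 1.00 |
| 4 | 0.94 | 1.00 |
| 5 | 0.82 | 0.97 |
| 6 | 0.67 | 0.90 |
| 7 | 0.50 | 0.78 |
| 9 | 0.24 | 0.50 |
| 10 | 0.15 | 0.37 |
| 12 | 0.05 | 0.18 |

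**How often that settles the verdict.** I assumed true shares without an increase and drew the arms as independent binomials. The best guess predicts success when the probability above is at least 0.5.

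| Assumed true share, investigational / reference | Verdict certain from pooled count (30; 45 per arm) | Best guess correct (30; 45 per arm) |
|---|---|---|
| 98% / 98% | 0.968; 0.965 | 0.997; 0.998 |
| 95% / 95% | 0.647; 0.530 | 0.943; 0.932 |
| 90% / 90% | 0.137; 0.047 | 0.772; 0.751 |
| 85% / 97% | 0.194; 0.079 | 0.485; 0.462 |

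**How much the open cut-off matters.** Attribute scores are 0, 0.5, 1, 2 and 3, so totals move in steps of 0.5 and a change of exactly 1.0 can occur. It is a failure if the cut-off is 1 or more, and not if it is more than 1. Suppose 15% of subjects rise by 1 or more, with 10 of those 15 percentage points at exactly 1.0. With 30 completers:
- cut-off 1 or more: P(Bin(30, 0.15) ≤ 3) = 0.32
- cut-off more than 1: P(Bin(30, 0.05) ≤ 3) = 0.94

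If only 5 points are at exactly 1.0, the second figure is P(Bin(30, 0.10) ≤ 3) = 0.65. These rates are illustrations, not figures from the documents.

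**How much an exclusion matters.** With 4 increases among 30 completers, 26/30 = 86.7% and the criterion fails. Excluding one subject with an increase gives 26/29 = 89.7%, still a failure. Excluding two gives 26/28 = 92.9%, a pass.

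**The case against.** The other side has a good case, and much of it stands.

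- **Most of the rule is fixed.** The 90% level, total score, time point and no-imputation rule are in the protocol. A reader might infer that who counts as completed is open too. It is not, because Protocol 4.4 defines completion.
- **Deviations do not reach the verdict by themselves.** There is one analysis population and no per-protocol set. Important deviations are counted and listed. A reader might infer that the visit-window review or the RLR list decides pass or fail. They can do so only through the exclusion of data, which is why the missing exclusion criteria are the point.
- **Pooled scores do not generally give the answer away.** They are least informative near the boundary, where a choice of rule would matter most, and a difference between the arms misleads the guess. This stands, with one qualification: someone viewing pooled scores need not know the verdict to see what a rule would do. If there are 7 pooled increases of 1 or more and 4 of them are exactly 1.0, moving to more than 1 leaves 3 and takes the chance of success from 50% to certainty.
- **The cut-off conflict needs reconciling whatever the date of sign-off.** True; an early date would not cure it. It matters here because it shows that content able to change the verdict does sit at the RAP stage.
- **The effect on readers is limited.** The analysis is descriptive and each subject's scores are listed, so either cut-off can be recomputed by anyone holding the listings.
- **No passage says that post-baseline scores go to the BDRM.** Nor does any passage withhold them.

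**Conclusion.** The point holds as a gap in safeguards. Masking the product code only weakly protects a success rule that is a proportion within one arm, and the plan's timing relies on that masking alone. With 30 completers per arm, pooled data settle the matter at 3 or fewer increases, make success unlikely (15% or less) at 10 or more, and say little around 7. With 45 per arm, success is certain at 4 or fewer and the even-chance point is 9. These figures rest on 1:1 allocation, equal numbers of completers and increases exchangeable between arms. If the arms differ, pooled data tell less.

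The content at risk is narrow: the cut-off, and the criteria for excluding data, including for out-of-window or deviating subjects.

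A reader might infer that rules were set with the outcome in view. The documents do not support that. The RAP sign-off date is not visible in the material available, and sign-off may have preceded every Visit 2 score. The change is a cheap improvement, not a defect that undermines the study.

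**What to change.** 1. In Protocol 12.2, replace the limit in "following finalization of the protocol and prior to study unblinding/analysis (as appropriate" with sign-off before the first Visit 2 dermatologist score is available to the RAP authors. If that was already the case, a dated statement saying so is enough.
2. By that date, state one cut-off in SAP 4.4.1.2 that is consistent with the success criterion in SAP 4.4.1.1, and record any departure from the protocol in Table 5-1.
3. By the same date, write the criteria for excluding data, including how out-of-window visits and important deviations are treated.
4. Make BDRM exclusion decisions from listings that omit post-baseline irritation scores. Ordinary cleaning of those scores should continue; removing them from all pre-lock review would go further than the problem requires.
5. Label any later change to these rules as post hoc in the study report.

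The cost is earlier completion of a short descriptive plan, a filtered set of listings and slightly less flexibility late in the study. Subjects, visits and sample size do not change.

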12.2.1 Definition of Analysis Populations

The Safety population will comprise all randomized subjects who receive at least one dose of the study product. This population will be based on the product the subject actually received.

All assessments of safety will be based on the safety population.

12.2.2 Exclusion of Data from Analysis

Exclusion of any data from the analyses will be determined during a Blind Data Review Meeting prior to database lock. Any reasons for exclusion from an analysis population will be listed, if applicable. No data will be excluded from any analysis post database lock. No decisions regarding data exclusions from any analysis will be made post database lock.

12.2.3 Demographic and Baseline Characteristics

Age will be summarized using descriptive statistics such as means, medians and standard deviations. Gender, race and Fitzpatrick skin type will be summarized using frequency counts and percentages for the safety population.

12.2.4 Study Drug/Product Compliance

Compliance to the study product use will be tabulated and summarized for the safety population.

12.2.5 Prior and Concomitant Medications

Prior medications, concomitant medications and significant non-drug therapies taken during treatment will be listed for the safety population.

12.2.6 Primary Analysis(es)

The primary endpoint will be the change from baseline (prior to any product application) in dermatologist signs and symptoms of cutaneous irritation total score following 21 (+2) days of product use. The primary analysis will be performed using the Safety population.

The dermatologist assessment of signs and symptoms of cutaneous irritation total score will be calculated as the sum of the individual dermal response attributes (erythema, dryness, scaling, and edema). The change from baseline in the total score will be summarised by number and percentage of subjects by visit for each treatment group. No formal statistical inference will be performed.

In addition, the individual attribute responses and the total score will be listed for each subject by visit and by treatment group.

12.2.7 Secondary Analysis(es)

The key secondary endpoint will be the change from baseline (prior to any product application) in the ophthalmologist signs and symptoms of ocular irritation total score following 21 (+2) days of product use.

The ophthalmologist assessment of signs and symptoms of ocular irritation total score will be calculated as the sum of the individual ocular response scores (eczema of the eyelid, conjunctivitis, follicles, chemosis conjunctivae). The change from baseline in the total score will be summarised by number and percentage of subjects by visit for each treatment group. No formal statistical inference will be performed.

In addition, the individual attribute responses and the total score will be listed for each subject by visit and by treatment group.

Further secondary endpoints are change from baseline (prior to any product application) in the total subject self-assessment scores for signs and symptoms of cutaneous irritation and ocular irritation at 1-2 hours and 21 (+2) days of product use.

All secondary analyses will be performed using the Safety population.

12.2.8 Safety Analysis(es)

Adverse events will be tabulated according to the current version of the MedDRA.

Frequencies and percentages will be presented overall, for each system organ class, and for each preferred term. Summaries of treatment-emergent AEs, treatment-related AEs, AEs leading to discontinuation, and serious AEs will be presented for each of the test products.

12.2.9 Other Analysis(es)

No other analyses will be performed for this study.

12.2.10 Handling of Dropouts and Missing Data

Missing data will not be replaced or imputed. Dropouts will be included in analyses up to the last assessments at the point of discontinuation.

12.2.11 Interim Analysis

No interim analysis is planned for this study

13 STUDY GOVERNANCE CONSIDERATIONS

13.1 Quality Control

In accordance with applicable regulations including GCP, and GSK CH procedures, GSK CH or designee (i.e. third-party vendor) monitors will contact the site prior to the start of the study to review with the site staff the protocol, study requirements, and their responsibilities to satisfy regulatory, ethical, and GSK CH requirements.

When reviewing data collection procedures, the discussion will include identification, agreement and documentation of data items for which the CRF will serve as the source document.

GSK CH or designee will monitor the study and site activity to verify that the:

- Data are authentic, accurate, and complete.
- Safety and rights of subjects are being protected.
- Study is conducted in accordance with the currently approved protocol and any other study agreements, GCP, and all applicable regulatory requirements.

The extent and nature of monitoring will be described in a written monitoring plan on file at GSK CH. The investigator (or designee) agrees to allow the monitor direct access to all relevant documents and agrees to co-operate with the monitor to ensure that any problems detected in the course of these monitoring visits are resolved.

13.2 Quality Assurance

To ensure compliance with GCP and all applicable regulatory requirements, GSK CH may conduct a quality assurance assessment and/or audit of the site records, and the regulatory agencies may conduct a regulatory inspection at any time during or after completion of the study.

In the event of an assessment, audit or inspection, the investigator (and institution) must agree to grant the advisor(s), auditor(s) and inspector(s) direct access to all relevant documents and to allocate their time and the time of their staff to discuss the conduct of the study, any findings/relevant issues and to implement any corrective and/or preventative actions to address any findings/issues identified.

The investigator(s) will notify GSK CH or its agents immediately of any regulatory inspection notification in relation to the study. Furthermore, the investigator will cooperate with GSK CH or its agents to prepare the study site for the inspection and will allow GSK CH or its agent, whenever feasible, to be present during the inspection. The investigator will promptly apply copies of the inspection finding to GSK CH or its agent. Before response submission to the regulatory authority, the investigator will provide GSK CH or its agents with an opportunity to review and comment on responses to any such findings.

The sponsor will be available to help investigators prepare for an inspection.

